8.3.2 Stage 2: PICSO treatment

1. In patients with IMR >40 who assent to PICSO treatment, the PICSO device will be deployed as already previously described in the literature [22] (Section 9.2). The overall duration of PICSO will be no less of 60 minutes up to a maximum of 90 minutes in order to ensure a PICSO delivery dose of 800 mmHg.

8.3.3 Stage 3: Stenting

1. Stenting is performed as usual clinical practice.
2. Post-dilation is left to operator's discretion, as in clinical routine.
3. At the end of the procedure a final reassessment of coronary physiology parameters is performed again as previously described.

Blood samples may be taken, (by 5 or 10 ml syringes), at the following time-points, from both peripheral vein (V), using the venous cannula, from the coronary sinus (CS) using a CS sampling catheter, or the PICSO delivery sheath, and from the coronary artery (C) either via the guide catheter used for the procedure or an aspiration catheter placed through the guide catheter:

Sampling point (1): beginning of procedure	V, C
Sampling point (2): placement of PICSO device	V, CS, C
Sampling point (3): end of procedure	V, CS, C
Sampling point (4): end of PICSO treatment period	V, CS,
Sampling point (5): 6 hours after 1 st stent deployment	V

For patients in whom an aspiration catheter or protection device is used during PCI, blood, thrombus and/or atheromatous plaque material may be retrieved during the procedure. These materials, which are usually discarded, will be retained for analysis. Data on the PCI procedure and any device or technology used will be collected.

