The Prepare-PICSO study represents the first-in-man experience with the PICSO device [21]. On a small sample of 15 patients with stable angina the PICSO treatment showed to be firstly safe and, as observed in the animal models, was associated to a significantly increase in coronary sinus pressure as well in mean CW pressure in the distal left anterior descending (LAD) coronary artery [21].

These findings have triggered the Prepare-RAMSES study in which PICSO treatment was investigated for the first time in man in patients with STEMI [22]. The results of the study have been recently published. The study was initially designed to include 30 patients with anterior STEMI with PICSO treatment for 90 minutes after the completion of primary percutaneous coronary intervention (PPCI). The study enrolled only anterior STEMI since expected to be responsive to the PICSO device, being mainly the anterior wall of the myocardium drained by the coronary sinus. The device resulted to be safe, with a median implantation time of 12 minutes. The primary endpoint was the reduction in IS at cardiac magnetic resonance (CMR) at 2-4 days and 4 months. The PICSO group was compared with a matched control group of patients.

Although the study did not show an overall difference in the reduction in IS in the PICSO group [22], IS reduction appeared to be significantly related to the quantity of PICSO treatment (pressure achieved in the coronary sinus x time of treatment) and significantly higher in the small subgroup of patients receiving high PICSO quantity.

It is possible that the study did not reach the primary endpoint due to some limitations in its design. First of all the small sample size has to be acknowledged, since the investigators managed to fully deliver the PICSO treatment only to 12 patients (63% of the initially intended sample size). Moreover, the study

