10.2 Device Safety

PICSO treatment is safe. Potential complications associated to PICSO may include:

- a) Bleeding due to damage to the coronary sinus where the PICSO catheter is placed
- b) Bleeding in the groin from the femoral vein access.
- c) Long term blockage of the coronary sinus where the PICSO catheter sits.
- d) Helium leak from the catheter into the blood. A leak of helium into the patient could occur with a balloon rupture or hole. However the risk is significantly mitigated since the system can automatically detect any leakage and stop the procedure. The maximum helium volume that could enter the patient using the PICSO system is less than 10 ml. This volume is approximately 1/3 of the volume that could leak from a bursting intra-aortic balloon pump (IABP) catheter, that are used in routine clinical practice in the aorta (i.e arterial circulation), whereas the PICSO catheter is used exclusively in the venous

circulation.. A helium leak from the PICSO system is therefore regarded to constitute a low risk to the patient.

Data about PICSO are continuously increasing and in the two main studies performed in man so far (PREPARE-PICSO and PREPARE-RAMSES) only one procedure adverse event (tamponade secondary to coronary sinus perforation) has been described. This rate (<3%) of complication is further lower than that associated to the routine elective electrophysiological procedures to the coronary sinus in the context of tachycardia ablation or cardiac resynchronization therapy.

It is possible that the PICSO balloon may be dislodged from the coronary sinus into the right atrium. This event has no known safety implications for the patients, but it may affect the efficacy of the PICSO treatment. The PICSO console will detect the occurrence of such event and alert the clinical team. In such a scenario balloon repositioning will only be considered if the treatment time-interval is less than 60 minutes. In order to minimize the risk for the patient, repositioning will be performed under fluoroscopic guidance in the catheterization laboratory. Once the balloon is repositioned, the PICSO treatment will be continued to achieve a minimum total treatment time of 60 minutes to a maximum of 90 minutes from the time of stent deployment.

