All the investigators using the PICSO device will undergo a specialist training programme completion, including the performance of the first cases under the supervision of a proctor expert. Educational training sessions for use of the PICSO will be provided to all clinical staff (nurses, radiographers, physiologists) involved in the care of patients who have received PICSO. Patients undergoing PICSO treatment will be strictly monitored, according to the standard clinical care guidelines, during and after the PICSO treatment in order to minimize or to early detect possible issues associated to the treatment. After the procedure, when the PICSO treatment is still ongoing, the patients will be monitored in the Recovery Assessment Area in order to guarantee a rapid access to the Catheterization Laboratory, if required.

The additional x-rays used for the placing of the device is extremely low in the context of the exposure associated to the standard primary PCI procedure. The radiation dose associated with the placement

of the device is estimated to be 4.3 mSv, which is approximately equivalent to 22 months exposure to UK background radiation. This may theoretically be associated with an increased lifetime risk of developing a cancer of 0.06%. This compares with the risk of developing a cancer in the general population of around 30% to 40%. So overall this represents a very small addition to the underlying cancer risk from all causes.

The radiation exposure in case of repositioning the PICSO balloon is estimated to be less than that associated with the device implantation. Therefore patients undergoing repositioning would have a global radiation dose associated to the PICSO device of no more of 8 mSv.

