12.2 Analysis of Endpoints

In keeping with our usual practice we will obtain expert statistical advice from the Centre for Statistics in Medicine (or equivalent) for each specific task. Summary statistics, including means, medians, and

variances, will be calculated at each time point and for each type of data (e.g. parameters derived from coronary physiology and CMR). The distribution of the levels will be described. It may be necessary to log transform the data before further statistical analysis. For each parameter an analysis of variance will be carried out at each time point.

Control group in OxAMI-PICSO study is represented by a highly matched group of patients underwent to primary PCI, with a prestenosing IMR > 40 and with available 24 hours recath and 24-48 hours/6 months CMR data. Matching will be performed by application of a propensity score matching analysis including the following predictors in the model: age, sex, pain to wire time, thrombotic burden (assessed as angiographic thrombus score), thrombus aspiration performance, stent volume, glycoprotein IIbIIIa inhibitors adoption.

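### End-of-PCI IMR and FFR are read during ongoing PICSO treatment in treated patients and with no device in controls, yet section 12.2 plans to analyse them like any other time point

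*Combined protocol and SAP*

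**What the plan says.** Physiology is measured before stenting, after stenting and at 24 hours (section 9.4). For the second of these, section 8.3.3 states: "At the end of the procedure a final reassessment of coronary physiology parameters is performed again as previously described".

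PICSO starts before stenting (section 8.3.2), and "The overall duration of PICSO will be no less of 60 minutes up to a maximum of 90 minutes". Section 8.3.3 gives end of procedure as sampling point 3 and then lists "Sampling point (4): end of PICSO treatment period". Section 10.2 adds: "After the procedure, when the PICSO treatment is still ongoing, the patients will be monitored in the Recovery Assessment Area".

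The controls are matched OxAMI patients who went through the other study procedures without PICSO (section 5).

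On analysis, section 12.2 says "For each parameter an analysis of variance will be carried out at each time point". It gives coronary physiology as an example of the data covered and exempts no time point. The physiology endpoint listed in section 5 is CFR, FFR and IMR at 24 hours. The listed primary outcomes are CMR measures at 24-48 hours.

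**The concern.** Section 4.2 reports that in the first-in-man study PICSO was "associated to a significantly increase in coronary sinus pressure as well in mean CW pressure in the distal left anterior descending (LAD) coronary artery". It also gives redistribution of blood flow as one of the mechanisms of benefit. Section 9.4 computes FFR as Pd/Pa and IMR as hyperaemic Pd times hyperaemic mean transit time, with no term for venous pressure or device state.

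A treated patient measured at end of PCI may therefore give a reading that carries a mechanical contribution from the device. A control's reading cannot. If the analysis in section 12.2 is run at that time point, a difference in either direction could be reported as microvascular benefit or harm when part of it belongs to the device. The primary objective mentions coronary physiology without a time limit, so such a result could find its way into the main account of the trial.

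**Working it through.** The plan gives no figure for this comparison, so there is none to reproduce. The check is one of timing, then of what can be said about size.

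**1. Order of events in the text.** In section 8.3.3 the end of the procedure precedes the end of PICSO. Section 10.2 has patients in recovery with PICSO continuing. Appendix A agrees: its End of PCI column comes before PICSO stop, and it appears to mark both PICSO and physiology at End of PCI. The table is broken in the copy read, so the conclusion rests on the two text sections.

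**2. Order of events from the plan's durations.** Inputs:
- PICSO duration D: 60 to 90 minutes (section 8.3.2)
- typical PCI about 60 minutes, lengthened by about 20 (section 16.2)
- median deployment time 12 minutes, interquartile range 9-18 (section 10.1)

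Total procedure T = 60 + 20 = 80 minutes. If PICSO starts at minute s, it has run T − s minutes at end of PCI, and D − (T − s) minutes remain. The start times below are assumed.

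| s (assumed) | PICSO run at end of PCI | Left to 60-minute minimum | Left to 90-minute maximum |
|---|---|---|---|
| 20 | 60 | 0 | 30 |
| 30 | 50 | 10 | 40 |
| 40 | 40 | 20 | 50 |

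PICSO is over by end of PCI only if s ≤ T − D. At the minimum, s ≤ 80 − 60 = 20. At the maximum, s ≤ 80 − 90 = −10, which is impossible. Even in the first case, a 12-minute deployment leaves 20 − 12 = 8 minutes (2 to 11 across the interquartile range) for angiography, wire crossing, restoring flow and pre-stenting physiology. Overlap is the normal case.

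For repositioned balloons, section 10.2 describes "a minimum total treatment time of 60 minutes to a maximum of 90 minutes from the time of stent deployment", whereas section 8.3.2 gives an overall duration. The two must be reconciled. Counting from stent deployment would only lengthen the overlap.

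**3. Is the comparison planned?** Section 12.2 does not name the factor in the analysis of variance. At a single time point, the only contrast that section sets up is PICSO against matched controls. After stenting is one of the three physiology time points in section 9.4.

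**4. Size and direction.** Writing Tmn for mean transit time, IMR = Pd × Tmn and FFR = Pd/Pa. If the device raised Pd alone, both would rise, which looks unfavourable on IMR and favourable on FFR. If it shortened Tmn alone, IMR would fall and FFR would not move. The documents give no on-device Pd or transit time, so neither sign nor size can be derived.

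**The case against.** The strongest reply is that the listed physiology endpoint is already at 24 hours, with the device off. End-of-PCI physiology is not a listed endpoint, so the problem sits in an unlisted analysis reached through one generic sentence. That is correct and it limits the point. It does not remove it, because the sentence covers this time point.

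The documents also do not say what the balloon is doing during the reading. Section 10.1 describes cycles of inflation, at most 30 seconds each, separated by deflations of at least 3 seconds. A pause might be made in practice. The console already shows balloon state and stores its data for each patient. This stands: what is established is an ongoing treatment period, not an inflated balloon.

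Four stronger readings are tempting and should not be drawn:

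- **A numerical shift in IMR.** A reader might carry the reported pressure rise into Pd and compute one. That rise was in wedge pressure, in 15 patients with stable angina, not in hyperaemic Pd in an open, freshly stented artery. With Pa unchanged, a 20% rise in Pd would push FFR above 1 from any start above 1/1.2 = 0.83, and a 10% rise from any start above 1/1.1 = 0.91.
- **Bias in CFR.** CFR is the ratio of two transit times from one session, so a proportional device effect would cancel. The documents show no mechanism for a bias.
- **A distorted primary result.** The primary objective mentions physiology, but the listed primary outcomes are CMR measures taken after PICSO has ended.
- **A distorted 24-hour endpoint.** The synopsis speaks of the evolution of physiology at 24 hours. A reader might take end of PCI as the starting value, but no baseline is stated.

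It can also be said that adjusting for pre-stenting IMR is a separate modelling choice. That is partly fair. It is still the natural companion to the change: it is the last reading taken without the device in both groups, and the propensity model omits it.

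**Conclusion.** The point holds, as a minor one. Followed as written, section 12.2 compares IMR and FFR taken during PICSO treatment with IMR and FFR taken without any device. A difference at end of PCI could not be attributed to microvascular recovery alone.

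This rests on two assumptions: that the reading is taken without an unwritten pause of the device, and that the pressure and flow effects described in section 4.2 reach the measured quantities to some degree. The size and direction of any distortion are unknown. The 24-hour physiology endpoint and the CMR endpoints are measured with the device off and are not affected.

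**What to change.** In section 12.2:

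- State that the between-group test of coronary physiology is the listed 24-hour measurement, adjusted for pre-stenting IMR. Both groups have this value, since selection requires it to exceed 40. It is not among the propensity predictors, so the groups can still differ in it above that threshold.
- State that end-of-PCI values in PICSO patients are reported as on-device and descriptive.

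On the CRF, record the clock time of the end-of-PCI reading so that it can be linked to the balloon state the console stores. Separately, reconcile the two descriptions of PICSO duration in sections 8.3.2 and 10.2, so that device status at each reading is clear.

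The cost is a short amendment to section 12.2 and one recorded time, with no extra patients or procedures. What is given up is a formal end-of-PCI test for the three physiology parameters, IMR, FFR and CFR.

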10. IDENTIFICATION & DESCRIPTION OF THE INVESTIGATIONAL DEVICE

10.1 Device description

The PICSO Impulse System consists of the PICSO Impulse console (101.100.000.000) and PICSO impulse catheter (300.100.000.010) by Miracor Medical Systems ([name]).

PICSO Impulse Console

PICSO Impulse Catheter

Each PICSO Impulse catheter will have a serial number, which will be recorded for traceability during and after completion of the study.

The PICSO Impulse catheter presents a balloon at the distal end. The balloon inflates and deflates cyclically once deployed in the coronary sinus, leading to intermittent coronary sinus pressure increase. This intermittent increase in coronary sinus pressure leads to an improved perfusion of the ischemic

area with potential benefit in terms of myocardial salvage through 3 mechanisms: 1) redistribution of blood flow from the remote myocardium to the border zone of the ischemic myocardium [14]; 2) enhanced wash out of noxious, inflammatory factors and embolic material across the microvascular bed (suction effect upon balloon release) [15]; 3) improvement in collaterals through release of vascular growth factors as consequence of venous pressure increase [16-17].

The PICSO Impulse catheter is a 8F double lumen catheter with a 15.5x20mm long balloon at the distal end. The catheter is connected to the console through two pneumatic tubes in which helium is shuttled to and from the balloon. In addition, the coronary sinus pressure is monitored through the center lumen of the catheter. The catheter is placed in the coronary sinus over a 0.025' wire by a 8.5Fr pre-shaped delivery long steerable sheath (Oscor Destino Steerable Sheath DS856750/22) inserted in the femoral vein. Femoral vein access is obtained as routine practice according to Seldinger technique. Once the catheter is placed, the guidewire is removed and the steerable sheath is retracted in the right atrium for support. PICSO deployment median time has been estimated to be of 12 minutes (Interquartile Range 9-18 minutes)

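### Coronary sinus samples may be drawn through a sheath that the protocol has by then moved to the right atrium, so specimens taken that way would carry the wrong site label

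*Combined protocol and SAP*

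**What the plan says.** Section 8.3.3 describes optional blood sampling around the procedure. CS blood is to be taken "from the coronary sinus (CS) using a CS sampling catheter, or the PICSO delivery sheath". The schedule asks for CS blood at three of its five points:

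- "Sampling point (2): placement of PICSO device"
- "Sampling point (3): end of procedure"
- "Sampling point (4): end of PICSO treatment period"

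No route is assigned to any of these points.

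Section 10.1 identifies the delivery sheath as an "8.5Fr pre-shaped delivery long steerable sheath (Oscor Destino Steerable Sheath DS856750/22) inserted in the femoral vein". It then says where that sheath goes: "Once the catheter is placed, the guidewire is removed and the steerable sheath is retracted in the right atrium for support".

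Section 10.2 allows for treatment continuing outside the laboratory: after the procedure, "when the PICSO treatment is still ongoing, the patients will be monitored in the Recovery Assessment Area".

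**The concern.** Section 8.3.3 treats the sheath as a way of reaching the coronary sinus, whereas section 10.1 leaves it in the right atrium for the whole period in which PICSO runs. Right-atrial blood mixes coronary sinus blood with the rest of the venous return. A specimen drawn there under a CS label does not measure what the label says.

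This matters because one stated mechanism of PICSO (sections 4.2 and 10.1) is washout of noxious and inflammatory factors from the microvascular bed, and the secondary objective in section 5 asks how PICSO may modify biomarkers. Serial CS samples are the most direct look at that. If the point 2 sample is true CS blood and the later ones are right-atrial, the change of site coincides with the treatment. The resulting shift is systematic, so more patients would not average it away.

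**Working it through.** The plan gives no figure to reproduce on this point. The check is a comparison of sections, followed by the direction of the bias.

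**1. Are points 3 and 4 after retraction?** Yes. Section 8.3.2 places the device before stenting (8.3.3), and 10.1 ties retraction to catheter placement. End of procedure and end of PICSO both come later. Appendix A is consistent: it marks PICSO at its start, at the end of PCI and at its stop.

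**2. Where does each sample come from?**

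| Point | Through a CS sampling catheter | Through the delivery sheath |
|---|---|---|
| 2, placement | Coronary sinus | Coronary sinus if drawn before retraction with the tip there; right atrium if drawn after. Timing is not stated |
| 3, end of procedure | Coronary sinus | Right atrium, unless the sheath is re-advanced |
| 4, end of PICSO | Coronary sinus | Right atrium, unless the sheath is re-advanced |

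**3. Does other text resolve it?**

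- No section describes re-advancing the sheath for sampling or restricts sheath sampling to the time before retraction.
- Section 11.10 lists sampling routes only in general terms, including a coronary sinus catheter.
- Section 9.5 covers laboratory handling.
- Appendix A has one blood-sample row with no site.
- Sections 8.3.3 and 9.1 call for data on procedures and devices. That might capture the route but does not ask for tip position.
- Section 10.1 describes one lumen that stays in the coronary sinus, the centre lumen of the PICSO catheter. It is described for pressure monitoring, and 8.3.3 does not name it for sampling.

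**4. Direction of the bias.** Let *r* be the ratio of CS to systemic venous concentration and *p* the share of CS blood in what the sheath draws. Then

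right-atrial / systemic = (1 − p) + p·r = 1 + p(r − 1).

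The true CS excess is r − 1 and the observed excess is p(r − 1). For any p below 1 the excess shrinks, and a deficit (r below 1) shrinks likewise.

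- *Mimicking an effect:* with r constant and above 1, a true CS sample at point 2 followed by a right-atrial sample at point 3 shows an apparent fall from r to 1 + p(r − 1).
- *Hiding an effect:* if washout truly raises the ratio from r to a larger r′ (with r above 1), the series still appears to fall whenever p < (r − 1)/(r′ − 1).

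**5. Size.** The documents give neither *p* nor *r*, so the dilution cannot be calculated.

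**The case against.** The best defence is that 8.3.3 names the compartment first and the tools second. On that reading, the sheath serves while it is delivering the catheter and a CS sampling catheter serves afterwards, so blood knowingly drawn from the right atrium would not comply. The dimensions lend some support: an 8F catheter in an 8.5Fr sheath probably leaves little room to draw around it, which favours sampling before the catheter goes in. The study is single-centre with proctored operators. The centre lumen of the PICSO catheter could also supply true CS blood in the Recovery Assessment Area, and the wording of 11.10 does not exclude it.

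Part of this stands. A reader might infer that the site would label all such specimens CS, or that two of the three CS points are always exposed once the sheath is used. Neither follows: staff could use the sheath at point 2 only, or a CS catheter throughout. Nor does the Recovery Assessment Area make true CS sampling at point 4 impossible, given the centre lumen and the rapid access to the laboratory that 10.2 describes.

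What does not stand is the claim that the text is already clear. The sensible reading has to be supplied by the reader, because 8.3.3 lists the sheath without limit at all three points and no section requires the information needed to identify a right-atrial specimen later.

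**Conclusion.** The two sections conflict and should be reconciled. The conclusion is conditional: specimens drawn through the retracted sheath are right-atrial; those from a CS sampling catheter are not affected; point 2 is ambiguous rather than clearly affected. It assumes that the sheath stays where 10.1 puts it.

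The reach is limited. CS sampling is optional. The biomarker endpoint in section 5 is set at PCI, 24/48 hours and 6 months and names no CS specimen or gradient; section 12.2 plans no CS-specific analysis; and no section says that the historical controls had CS samples. A reader might infer that the secondary biomarker endpoint as a whole is compromised. The documents do not support that: the exposure is confined to exploratory within-patient CS comparisons, and the primary CMR endpoint is not involved.

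A reader might also want a figure. Assuming that CS flow is 3–10% of venous return and that mixing is complete would suggest a loss of 90–97% of the CS excess. But that is only 1 − p, the assumed share restated (1 − 0.10 = 0.90; 1 − 0.03 = 0.97), and the documents support neither assumption. The direction of the dilution is secure; its size is unknown.

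**What to change.** Reconcile 8.3.3 with 10.1 as follows:

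- Limit CS samples drawn through the delivery sheath to the time before it is retracted.
- State which lumen is used for CS samples at points 3 and 4.
- Record the sampling lumen and tip position on the CRF for each specimen.
- Code blood from the retracted sheath as right-atrial and keep it out of the CS time course. It can be reported separately under its own label.

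These changes concern how specimens are defined, recorded and analysed, not how PICSO is delivered. They need protocol wording and additional CRF fields. The downside is that fewer specimens may count as CS at points 3 and 4; any dropped because they came from the retracted sheath would not have been valid CS measurements.
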